### Software:

Analyses will be conducted using Stata (StataCorp LP; College Station, TX) [or specify alternative if applicable].

[figure not shown]
## Figures

Figures will be adapted from Abdallah et al. (2017) to illustrate perceptual and physiological responses during constant-load exercise testing. These will include:

- **Panels a–c:** Symptom ratings (breathlessness intensity, breathlessness unpleasantness, and leg discomfort) plotted against time during exercise for menthol and placebo conditions.
- **Panels d–f:** Post-dose differences (menthol minus placebo) at isotime and peak exercise for breathlessness intensity, unpleasantness, and exercise endurance time (EET), including individual participant data and group means with 95% CIs.
- **Panels g–i:** Distribution of individual responses and indication of clinically meaningful thresholds (e.g., minimally clinically important difference).

These figures will visualize symptom trajectories, treatment effects, and variability across participants, highlighting both statistical and clinical significance.

**Figure 1: CONSORT diagram showing the flow of participants through each stage of the study**

**Table 1: Baseline participant characteristics ( t-test for continuous variables with normal distribution, ranksum test for continuous non-normal variables and chi-square for categorical variables).**

Parameter	Menthol first	Placebo first	All participants
N (%)			
Male:female (n)			
Age, mean years (SD)			
Height (cm)			
Weight (kg)			
BMI kg/m  , mean (SD)			
Smoking history, pack-years (SD)			
Physical activity during normal week			
Post-bronchodilator pulmonary function (spirometry)			
FEV 1 , L (SD)			
FEV 1 , % predicted (SD)			
FVC, L (SD)			
FVC, % predicted (SD)			
FEV 1 /FVC, L (SD)			
FEV 1 /FVC, % of predicted (SD)			
Breathlessness and health status			
mMRC 0-4			
CAT total Score			
CAT breathlessness			
CAT activity limitation			
MDP A1 total			
Dyspnea 12			
Dyspnea severity likert			
SF12 q1 – q12			
Change between visit 1 and 2 (GIC-scale)			
Change between visit 2 and 3 (GIC-scale)			
Underlying conditions			
Ischaemic heart disease			
Angina Pectoris			
AF			
Heart failure			
Hypertension			
Hyperlipidemia			
Diabetes			

Obstructive sleep apnea			
Asthma			
Other lung disease			
Tuberculosis			
Rheumatic disease			
Stroke			
Cancer			
Depression or anxiety			
None			
Other			
Medications			
Diuretics			
Beta blocker			
Calcium antagonist			
Renin-angiotensin system blocker			
Insulin			
Other diabetic medication			
Anti hyperlipidemic drug			
Inhalators for COPD/asthma			
Anticoagulants			
Antidepressants/anxiolytics			
Sleep medication or other benzodiazepines			
Other			
COPD medication			
LABA+LAMA			
LABA+LAMA+ICS			
LABA			
LAMA			
LABA+LAMA+Daxas			
LABA+LAMA+ICS+Daxas			
Physiological responses at incremental cycle test (visit 1)			
Cycle exercise time (min)			
Workload, W			
Workload, % of predicted			
Heart rate, beats/min			
Breathing frequency (breaths/min)			
SpO 2 (%)			
V O2 , mL/kg/min,			
V O2 (% of predicted),			
V'CO 2 (ml/kg/min)			

RER			
$V'_{E, L/min}$			
$V_T, L$			
$V'_E/V'_{CO_2}$			
Perceptual responses during test (visit 1)			
Breathlessness intensity, Borg units			
Breathlessness discomfort, Borg units			
Leg discomfort, Borg units			
Reasons for stopping exercise (visit 1)			
Breathlessness (n)			
Leg discomfort (n)			
Breathlessness and Leg discomfort (n)			
Breathlessness ratings after test (visit 1)			
MDP (A1 + dimensions)			
D12			
Self-reported motivation for completing test (visit 1)			

**Table 2:** Effect of menthol versus placebo on physiological and perceptual responses at a standardized submaximal time during constant-load exercise testing (isotime) and at the symptom limited peak of constant-load exercise testing among individuals with Chronic obstructive pulmonary disease. (t-test for continuous variables with normal distribution, ranksum test for continuous non-normal variables and chi-square for categorical variables). **(Visit 2 and 3)**

Parameter, mean (SD)	Rest			Isotime			Peak		
	Menthol	Placebo	Mean difference (95% CI)	Menthol	Placebo	Mean difference (95% CI)	Menthol	Placebo	Mean difference (95% CI)
Physiological responses									
Cycle exercise time, min									
Heart rate, beats/min									
Breathing frequency, breaths/min									
SpO 2 , %									
V' O2 , ml/kg/min									
V' O2 , % of predicted									
V' CO2 (ml/kg/min)									
RER									
V' E , L/min									
V T , L									
V' E /V' CO2									
PETH CO 2									
Perceptual responses									
Breathlessness intensity (Borg CR10)									
Breathlessness unpleasantness (Borg CR10)									
Leg discomfort (Borg CR10)									
Significant breathlessness (>2, n (%))									
Reasons for stopping test									
Breathlessness (n)									
Leg discomfort (n)									

Breathlessness and Leg discomfort (n)								
Level of self-reported motivation								
Breathlessness ratings after tests								
MDP								
Dyspnea 12								

Mean differences are for menthol minus placebo.

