### Comparisons:

- Baseline characteristics will be compared using independent t-tests (continuous normal), Wilcoxon rank-sum tests (continuous non-normal), and chi-square tests (categorical).
- For CPET outcomes, within-subject comparisons between menthol and placebo will be performed using paired t-tests for normally distributed variables and Wilcoxon signed-rank tests for non-normal variables. Categorical outcomes will be analyzed using McNemar's test.
- CPET variables will be compared between conditions at isotime and peak exertion.

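### The Table 2 caption lists independent-sample tests for the within-participant menthol-placebo comparison, against the paired tests in the SAP's Comparisons section

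*SAP*

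**What the plan says.** The SAP's Comparisons section treats the two kinds of comparison separately.

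- Baseline, between sequence groups: "Baseline characteristics will be compared using independent t-tests (continuous normal), Wilcoxon rank-sum tests (continuous non-normal), and chi-square tests (categorical".
- Exercise-test outcomes, menthol against placebo: "within-subject comparisons between menthol and placebo will be performed using paired t-tests for normally distributed variables and Wilcoxon signed-rank tests for non-normal variables". For categorical outcomes: "Categorical outcomes will be analyzed using McNemar's test".

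The table shells carry their own test lists. Table 1, whose columns are the menthol-first and placebo-first groups, is captioned "Baseline participant characteristics ( t-test for continuous variables with normal distribution, ranksum test for continuous non-normal variables", with chi-square for categorical variables. Table 2 shows the menthol and placebo results at rest, isotime and peak from the two treatment visits. Its caption gives the same list: "t-test for continuous variables with normal distribution, ranksum test for continuous non-normal variables and chi-square for categorical variables). (Visit 2 and 3".

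**The concern.** Table 2 compares the same people under two conditions, yet its caption names the tests that the SAP reserves for comparing two different groups. Every Table 2 variable judged non-normal therefore has two prespecified tests (signed-rank and rank-sum), and so has every categorical row (McNemar and chi-square). Examples of the latter are "Significant breathlessness (>2, n" and the reasons for stopping. The table holds both primary outcomes, breathlessness intensity at isotime and exercise time. If either is judged non-normal, the SAP names two tests for a primary outcome and does not say which prevails.

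Two things are at stake. If the caption is followed, the pairing is discarded and a real effect may be missed. If the matter is left open, the test can be chosen after the data are seen, which an SAP is meant to prevent.

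**Working it through.** **Texts side by side**

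| Type of variable | Comparisons section, menthol v placebo | Table 2 caption | Comparisons section, baseline |
|---|---|---|---|
| Normal | paired t-test | t-test, pairing not stated | independent t-test |
| Non-normal | signed-rank | rank-sum | rank-sum |
| Categorical | McNemar | chi-square | chi-square |

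The second and third rows contradict each other outright. The first is an ambiguity. That the data are paired follows from the SAP's opening section, which defines isotime for a given participant across each constant-load test.

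**Inputs for the size.** The documents give the significance level (two-sided 0.05, Reporting section). They give no sample size, SD or within-person correlation r, so there is no figure in the plan to reproduce. Assumed: 20, 30 or 40 pairs; r from 0.3 to 0.8; equal variances; an effect that a paired t-test detects with 80% power.

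**Normally distributed variables, only if t-test is read as independent.** The variance of the mean difference is 2σ²(1−r)/n when paired and is estimated as 2σ²/n when pairing is ignored. The standard error, and the CI width, is then too large by 1/√(1−r). The unpaired statistic is the paired one times √(1−r), so on the paired scale the critical value becomes 1.960/√(1−r). With 80% paired power the expected paired statistic is 1.960 + 0.842 = 2.802. By the normal approximation:

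| r | SE ratio | Critical value, paired scale | Power | True type I error |
|---|---|---|---|---|
| 0.3 | 1.20 | 2.343 | Φ(2.802−2.343) = 68% | 1.9% |
| 0.5 | 1.41 | 2.772 | Φ(2.802−2.772) = 51% | 0.56% |
| 0.7 | 1.83 | 3.578 | Φ(2.802−3.578) = 22% | 0.04% |
| 0.8 | 2.24 | 4.383 | Φ(2.802−4.383) = 6% | 0.001% |

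**Non-normal variables: signed-rank against rank-sum.** Simulated power in bivariate normal data, 20,000 runs per cell:

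| Pairs | r = 0.5 | r = 0.7 | r = 0.8 |
|---|---|---|---|
| 20 | 78.2% → 51.4% | 78.2% → 25.6% | 78.0% → 10.4% |
| 30 | 78.5% → 50.4% | 78.1% → 24.1% | 79.0% → 9.2% |
| 40 | 78.3% → 49.7% | 77.9% → 23.2% | 78.2% → 8.3% |

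Rank-sum type I error was 0.74-0.85%, 0.10-0.16% and at most 0.04% in the three columns. At r = 0.3 (20 and 30 pairs) power falls only from about 78-79% to 66-67%.

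The result does not depend on normal data:
- Ratings rounded to whole numbers 0-10 (assumed mean 5, SD 2; 20 pairs): 76.1% → 50.3%, 76.0% → 25.5% and 74.9% → 10.6% at r = 0.5, 0.7 and 0.8.
- Log-normal data (20 pairs): 74% → 51% at r = 0.5 and 73% → 25% at r = 0.7.

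A separate run with 20 pairs, with the effect size taken from the normal formula (so that paired-t power is 76%), gave 74% → 46% at r = 0.5 and 74% → 22% at r = 0.7.

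**Categorical variables: McNemar against chi-square.** Assume 30 pairs: 16 positive under both conditions, 7 under placebo only, 0 under menthol only, 7 under neither.
- Exact McNemar uses the 7 discordant pairs: p = 2 × (1/2)⁷ = 0.0156.
- Chi-square compares 16/30 with 23/30. The pooled proportion is 39/60 = 0.65, and z = (7/30)/√(0.65 × 0.35 × 2/30) = 0.2333/0.1232 = 1.89, so p = 0.058 (no continuity correction).

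The same data fall on opposite sides of 0.05.

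**The case against.** The best defence is that this is a copying slip with little chance of doing harm. The Comparisons section is the only methods text on the choice of test. It is specific, it fits the design, and the reporting of menthol minus placebo agrees with it. The caption sits on an empty table shell and repeats the Table 1 wording. A paired t-test is a t-test, so a normally distributed primary outcome meets no contradiction. Table 2 has no p-value column, and choosing rank-sum over signed-rank alters neither a mean difference nor its CI. The power figures rest on assumed correlations, and at r = 0.3 the loss is modest. The binary example was chosen so that all discordant pairs go one way.

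Most of this stands as a limit on weight. The t-test is ambiguous, not contradicted. The CIs are affected only if they too are computed as for independent samples, which the SAP nowhere says. The figures are illustrations. But the contradiction itself is not answered. Rank-sum is not shorthand for signed-rank, nor chi-square for McNemar, and the Comparisons section uses these names for different purposes. The p-values still count, because the Reporting section defines significance by p < 0.05. The caption is also the instruction nearest to the output that the analyst fills in.

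**Conclusion.** The point holds. For non-normal and categorical variables the SAP names two incompatible tests for the same menthol-placebo comparison, and for normal variables the caption leaves the pairing unstated. A primary outcome is caught in the firm contradiction only if it is judged non-normal.

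The consequence is conditional on the caption being followed. Given positive within-person correlation it is conservative: lost power, not false positives. How much is lost depends on a correlation the SAP does not give, from roughly 12 percentage points at r = 0.3 (about 78-79% to 66-67%) to about 70 at r = 0.8 (about 78% to 8-10%), for an effect that the paired t-test would detect with 80% power. This should be corrected before analysis. It is not a flaw in the stated method, since the Comparisons section already has the right tests.

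**What to change.** Replace the test list in the Table 2 caption with the one in the Comparisons section: paired t-test for normally distributed variables, Wilcoxon signed-rank for non-normal variables, McNemar's test for categorical variables. Add to the table note that mean differences and 95% CIs are computed from within-participant differences, menthol minus placebo. The Table 1 caption can keep its rank-sum and chi-square list, because it compares separate groups. The cost is one caption edit in the SAP; no method, sample size or trial procedure changes.

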## Figures:

[figure not shown]

FIGURE 2 Effect of immediate-release oral morphine versus placebo on exertional breathlessness and exercise endurance in adults with advanced chronic obstructive pulmonary disease (COPD) and chronic breathlessness syndrome. Mean $\pm$ SEM a) breathlessness intensity ratings, b) breathlessness unpleasantness ratings and c) leg discomfort ratings at rest and during constant-load cycle exercise testing at 75% of peak incremental power output. Individual participant post-dose values and post-dose differences in d and g) breathlessness intensity ratings during exercise at isotime, e and h) breathlessness unpleasantness ratings during exercise at isotime and f and i) exercise endurance time, where red symbols with dashed horizontal lines in panels d, e and f) denote mean $\pm$ SEM. Dashed horizontal lines in panels g and i denote minimally clinically important difference for breathlessness intensity [36] and exercise endurance time [37].  $\Delta$ : post-dose difference (i.e., morphine minus placebo). \*:  $p<0.05$  versus placebo.

Example from Abdallah 2017 - panels (a,b och c) to be reported for each of “intensity,unpleasantness and leg discomfort”. To be presented as the above example but change “Morphine” to “Menthol”.

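### Does copying the example figure, with mean ± SEM in panels d–f, undermine the planned 95% CIs for the paired differences?

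*SAP*

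**What the plan says.** The SAP has two sections on figures.

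- **The Figures section after Software** says the figures will be adapted from a published trial and lists the panels. Panels d–f are "Post-dose differences (menthol minus placebo) at isotime and peak exercise for breathlessness intensity, unpleasantness, and exercise endurance time (EET"). They are to carry each person's data together with a mean and 95% CI for the group. Panels g–i are "Distribution of individual responses and indication of clinically meaningful thresholds". The set is meant to serve for "highlighting both statistical and clinical significance".
- **The closing Figures section, after Table 2,** reprints the legend of that trial's figure, which compared morphine with placebo. It describes "Individual participant post-dose values and post-dose differences in d and g) breathlessness intensity ratings during exercise at isotime", and continues in the same way for e with h and f with i. The group summary in d–f is given as "where red symbols with dashed horizontal lines in panels d, e and f) denote mean $\pm$ SEM". On thresholds it says "Dashed horizontal lines in panels g and i denote minimally clinically important difference for breathlessness intensity", and it names endurance time as well. A note below the legend first mentions panels a to c and then says "To be presented as the above example but change" the name of the drug.

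Two other parts of the SAP bear on the point. The Reporting section fixes the presentation of estimates as mean differences, menthol minus placebo, with 95% confidence intervals. Table 2 has a column for the mean difference and its 95% CI at rest, isotime and peak.

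**The concern.** A programmer given both sections could not satisfy both to the letter. One puts differences with 95% CIs in panels d–f. The other, as its legend reads, puts values for each condition with mean ± SEM there, moves the differences to g–i, and shows the breathlessness ratings at isotime only. The only adaptation the closing note spells out is the drug name.

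In a crossover trial the choice of bar matters to a reader. The SEM of a condition mixes in variation between people, which the paired comparison removes. Such bars do not show whether the interval for the effect excludes zero or reaches the threshold for a meaningful difference. Because the figure covers breathlessness intensity at isotime and endurance time, which are the primary and co-primary outcomes, a misleading display there would be worth correcting.

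**Working it through.** The SAP states no sample size, SD or correlation for this comparison, so there is no figure of its own to reproduce. Three checks apply.

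**1. How far do SEM bars differ from the planned intervals?**

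Inputs: 95% two-sided intervals (Reporting section). The sample size n and within-person correlation r are assumptions, as are equal SDs in the two conditions.

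(a) SEM against the 95% CI half-width of the *same* quantity: ratio = 1/t(0.975, n−1).

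| n | t | ratio |
|---|---|---|
| 10 | 2.262 | 0.442 |
| 20 | 2.093 | 0.478 |
| 30 | 2.045 | 0.489 |
| 60 | 2.001 | 0.500 |

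A bar of ±1 SEM covers about 66% at n = 10 and 67% at n = 20. For this comparison, about half is a fair description.

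(b) SEM of *one condition* against the 95% CI half-width of the *paired mean difference*: ratio = 1/(t × √(2(1−r))). This is the comparison the two sections actually set up. At n = 20:

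| r | √(2(1−r)) | ratio |
|---|---|---|
| 0 | 1.414 | 0.338 |
| 0.5 | 1.000 | 0.478 |
| 0.7 | 0.775 | 0.617 |
| 0.8 | 0.632 | 0.755 |
| 0.9 | 0.447 | 1.068 |

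Over n = 10 to 60 and r = 0 to 0.9 the ratio runs from 0.31 to 1.12. It is about one half only near r = 0.5. With strong within-person correlation the SEM bar is about as wide as the paired interval. The two bars measure different things, and the SAP does not allow a fixed ratio between them.

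**2. What would a literal copy of the example lose?**

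| Item | SAP panel list | Example legend |
|---|---|---|
| Panels d–f | differences, mean with 95% CI | values per condition (inferred), mean ± SEM |
| Panels g–i | individual responses, thresholds | post-dose differences (inferred), thresholds in g and i |
| Breathlessness ratings | isotime and peak | isotime |

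The content of d–f and g–i in the example is inferred from the pairing of letters in the legend, since the image is not available. On that reading a copy would still show each participant's difference, with the threshold line for intensity and for endurance time and a marker for p < 0.05. It would lack a group mean difference with a 95% CI, and the peak ratings.

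**3. Is the missing content fixed elsewhere?**

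Yes. Reporting requires the mean difference with 95% CI. Table 2 supplies it at isotime and at peak, with rows for breathlessness intensity, unpleasantness and exercise time. Comparisons sets the within-participant test. None of these refers to the figure.

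**The case for a change.** The strongest case for a change is that both sections are current text and give different contents for the same lettered panels. Announcing an adaptation does not say that SEM becomes a 95% CI. The Reporting rule covers estimates in general, so a figure of the two main outcomes without the paired interval would sit badly with it. The repair would cost a few lines.

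The literal mismatch stands, and one agreed panel list would be tidier. Two things weaken the rest. First, the conflict is not certain. The SEM wording belongs to another trial's legend, reprinted as an example, whereas the panel list is written for this trial. The instruction to follow the example comes straight after a remark about panels a to c, for which the panel list names no error bar, so it can be read as covering only those. On that reading nothing conflicts. Second, even on the stricter reading the reader is not left without the paired interval, because Table 2 gives it. Nor would per-condition SEM bars contradict that table, which also reports a mean and SD for each condition.

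**Conclusion.** No change to the plan is needed. The two sections do describe panels d–f differently if the copying instruction covers the whole figure, but the effect is confined to presentation. The outcomes, the tests, the mean differences, their 95% CIs and the 5% two-sided threshold are the same whichever description is followed. An analyst would sensibly follow the trial's own panel list and treat the morphine legend as a template for layout.

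A single width ratio cannot be attached to the mismatch. About half (0.44 to 0.50 for n of 10 to 60) holds only for an SEM and a CI of the same quantity. For the per-condition SEM against the paired interval the range is 0.31 to 1.12. It would also be too strong to say that a copied figure hides the paired effect: it would omit the mean difference with its interval but keep the individual differences.

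This rests on assumed values of n and r with equal SDs, on reading the example's panels from its legend alone, and on the interval in Table 2 coming from the within-participant analysis that the Comparisons section sets.
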